#### 9.2.1.1.2 European Surveillance of Congenital Anomalies (EUROCAT)

EUROCAT is a European network of population-based registries for the epidemiologic surveillance of congenital anomalies (EUROCAT, 2017). Started in 1979, the registry includes over 1.7 million births surveyed annually in Europe from 43 registries in 23 countries. Approximately 29% of the European birth population is covered by this network. These population-based registries facilitate the early warning of new teratogenic exposures, evaluate the effectiveness of primary prevention measures, and assess the impact of developments in prenatal screening.

Using 13 registries from the EUROCAT network from 01 January 1998 through 31 December 2011, Groen et al. reported an overall prevalence of congenital anomaly of 27.3 per 1000 births (range, 19.1–39.3 per 1000 births) (Groen et al, 2017). Of the 84,387 pregnancies with a known outcome (99.4%), 2.33% pregnancies were stillbirths, the proportion of early neonatal mortality (within 7 days of birth) was 2.37% and the proportion of late neonatal mortality (between 7 days to 27 days of life) was 0.84%.

### 9.2.1.1.3 Other Potential Sources

At the time of final report generation, any existing publicly available data sources (registries, cohorts) or published study results pertaining to migraine treatment exposures during pregnancy will be reviewed and considered for a summary of comparisons to results in this registry, where feasible. For example, results from the Sumatriptan, Naratriptan, and Treximet Pregnancy Registry may be a suitable external reference population for the internal comparator cohort ([Ephross and Sinclair, 2014](#)). No statistical comparisons will be made.

### 9.2.2 Study Period

The study start date will be the date of the first data collection: the date from which information on the first study patient is recorded in the study database. The end of the study will be the date from which the last data collected from the last patient is recorded in the study database. The total duration of per patient participation is up to 21 months and the total expected duration of the study is approximately 7 years.

### 9.2.3 Coordinating Center

This study will be conducted in the U.S. There will be at least 1 CC that is responsible for obtaining informed consent and all patient and HCP contacts during the study. See [Figure 1](#) (Data Flow Overview) for more information on CC data responsibilities.

### 9.2.4 Patient Eligibility

Women will be screened for eligibility criteria for each pregnancy, should they contribute more than one pregnancy in the Registry. Any within-patient pregnancy correlations will be accommodated in the analysis as part of the statistical analysis plan (SAP).

#### 9.2.4.1 Inclusion Criteria

- Patient consent obtained prior to enrollment
- Age 18 years or older at the time of signing the informed consent form (ICF)
- Currently pregnant
- The outcome of the pregnancy (ie, pregnancy loss or live birth) must not be known
- Confirmed clinical diagnosis of migraine by evaluation of the patient's treating physician (ie, neurologist, PCP), falling into 1 of 2 cohorts:
  - Erenumab-aooe exposed cohort: Documentation of exposure to erenumab-aooe from 3 months prior to LMP or at any point during the patient's pregnancy. Erenumab-aooe exposure information will be recorded including start and stop dates, dose, dosing frequency, reason for discontinuation (if applicable).
  - Internal comparator cohort: Documentation of no exposure to any CGRP mAb from 5 half-lives prior to LMP or at any point during the patient's pregnancy. Agrees to sign the Release of Medical Information Form permitting the study to

contact her HCPs (eg, PCP, neurologist [indication specialist], OB, nurse midwife) and the infant HCP (eg, pediatrician) for medical information

#### 9.2.4.2 Exclusion Criteria

- Women currently participating in another investigational device or investigational drug study, currently taking an investigational medicinal product, or having taken an investigational product within 3 months prior to LMP or during pregnancy. Other investigational procedures while participating in this study are excluded.
- Women exposed to any medication in the same pharmacological class as erenumab-aooe (ie, CGRP mAb) in the period from 5 half-lives prior to LMP through the end of pregnancy

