### **9.2.1 Study Population**

Currently pregnant women with clinically confirmed migraine in the U.S. who have been exposed to erenumab-aooe during the 3 months prior to their LMP or at any time during pregnancy will be considered for inclusion in the exposed study cohort. An internal comparator cohort will consist of currently pregnant women with clinically confirmed migraine who have not been exposed to any CGRP mAb, while secondary data sources will be used to compare results to external comparator cohort(s) representing the prevalence of birth defects in the general population (see [Section 9.2.4 Patient Eligibility](#)).

Women will be enrolled prospectively and may be enrolled from the post marketing setting or other clinical or observational studies of erenumab-aooe, unless prohibited by exclusion criteria noted in [Section 9.2.4.2](#). To reduce bias that may occur if outcome information is known prior to enrollment, women should be enrolled in the study as soon

as their pregnancy is known, preferably prior to any informative prenatal testing (where the knowledge of the primary study outcome of the pregnancy would be known – either normal or abnormal), and preferably in the first trimester before 20 weeks gestation. Women who receive any first trimester prenatal screening after enrollment (post-enrollment) will be included in the primary analysis. Decision criteria with regards to prenatal testing before enrollment (pre-enrollment) will be applied to the study population for inclusion into the primary analysis and is outlined in [Section 9.7.1.2](#). [Table 2](#) are the pertinent descriptions.

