### **During Follow-up of Pregnancy (estimated at 14, 21 and 34 weeks gestation)**

- Date of contact
- Reporter of information (eg, patient, PCP, OB, neurologist [indication specialist], nurse midwife, other)
- Current weight
- Changes in lifestyle risk factors (eg, smoking, caffeine consumption, alcohol use, illicit drug use)
- Number of migraines since last follow-up; frequency and duration, with or without aura, number of migraines requiring treatment, any prescription migraine treatments, and days of acute migraine treatments each month (by trimester)
- Changes in comorbid conditions
- Erenumab-aooe treatment (including start and stop dates, dose, dosing frequency, reason for discontinuation [if applicable])
- Current medications, including start and stop dates (eg, any other OTC migraine treatment(s), folic acid and other vitamins, herbal remedies or supplements, vaccinations, or other medications used to treat chronic conditions or comorbidities)
- Pregnancy status, if applicable:
  - Gestational age at contact
  - Any prenatal testing performed and results (eg, rubella titer, toxoplasmosis, venereal disease research laboratory test, hepatitis screen, ultrasounds, amniocentesis, maternal serum alpha-fetoprotein screen, glucose screen)
  - Pregnancy outcome (eg, live births, spontaneous abortions, stillbirths, elective or therapeutic terminations, reason for elective or therapeutic termination [eg, prenatal testing finding, risk to mother's health, undesired pregnancy], and autopsy results and pathology reports, if available)
  - Congenital malformations noted (including description and attribution)
- Patient AEs and SAEs (including event, start date, ongoing or end date, seriousness, severity, relationship to erenumab-aooe, outcome, action taken)

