#### 9.3.1 Exposure Assessment

The following criteria will be used to assign women to 1 of 2 cohorts, as determined by exposure to erenumab-aooe:

- **Erenumab-aooe Exposed Cohort:** Documentation of exposure to erenumab-aooe from 16 weeks prior (to allow for the half-life of erenumab-aooe) to LMP or at any point during the patient's pregnancy. Exposure information recorded will include start and stop dates, dose, dosing frequency, reason for discontinuation (if applicable).
- **Internal Comparator Cohort:** Documentation of no exposure to any CGRP mAb from 5 half-lives prior to LMP or at any point during the patient's pregnancy. Note: exposure assessments will not be determined for the external comparator cohort(s), as patient-level data is not available; these cohort(s) represent the prevalence of birth defects in the general population.

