#### 9.7.2.4 Analysis of the Primary and Secondary Endpoints

The prevalence of major and minor congenital malformations will be calculated using MACDP convention. Major malformations will be analyzed separately from minor malformations, with the primary analysis including only adjudicated major congenital malformations. The total prevalence will be calculated by dividing the number of adjudicated cases of each event (observed in live births, fetal deaths, elective or therapeutic terminations, and at any gestational age) by the total number of pregnancies (excluding spontaneous terminations and ectopic or molar pregnancies). The prevalence at birth will be calculated as number of cases observed in live births and stillbirths divided by the total number of births (stillbirths + live births). Data analysis for major congenital malformations will be based on first trimester exposure to erenumab-aooe.

The prevalence of pregnancy complications, including preeclampsia, pregnancy-induced hypertension, gestational diabetes, placenta previa, and preterm labor, will be summarized by dividing the number of each event by the total number of pregnant women.

The prevalence of spontaneous abortions will be calculated by dividing the number of fetal losses occurring before 20 weeks gestation by the total number of pregnancies.

The prevalence of elective and therapeutic abortion will be estimated similarly as separate outcomes.

Prevalence of preterm birth will be calculated by dividing the number of cases by the total number of births (stillbirths + live births). The prevalence of small-for-gestational-age will be calculated by dividing the number of cases by the total number of live births.

For growth and developmental delays, the prevalence will be calculated as the number of cases divided by the total number of live births.

Prevalence of primary and secondary outcome measures will be presented with 95% CIs for binomial proportion. The analyses summarized in this section will be performed on the erenumab-aooe exposed cohort and the internal comparator cohort consisting of pregnant women with migraine who were not exposed to erenumab-aooe; Characteristics can be matched or stratified in relation to the exposed cohort to control for important covariates such as maternal age (see [Section 9.7.2.5.1](#)).

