#### **9.9.1.2 Information Bias**

Patients who have been informed about a potential adverse pregnancy outcome prior to enrollment in the study may differentially recall their exposures during early pregnancy and may also have changed their exposures after learning of the outcome. This study plans to enroll both women where a fetal diagnosis has been made prior to enrollment in the registry, either positive or negative, for major congenital malformations that are unrelated to genetic or aneuploid disorders), and women with or without prenatal testing prior to enrollment that could determine the status of the fetus) (eg, amniocentesis, genetic testing, nuchal translucency screen, chorionic villus sampling, and late term ultrasound). The differential recall may lead to bias, which will be addressed with the stratification of primary and secondary outcomes by retrospective and prospective status. Additionally, the primary analysis will exclude women who have received first trimester prenatal screening in which either aneuploid disorders or genetic disorders that are known to cause major congenital malformations have been detected.

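### The CGRP cohort and exclusion criteria run past enrollment to the end of pregnancy, so the ever-exposed risk ratio for spontaneous abortion counts immortal time as exposed time

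*Protocol*

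**What the plan says.** - **Exclusion (Protocol 9.2.4.2).** Women exposed to another CGRP antibody are excluded if the exposure falls "in the period from 5 half-lives prior to LMP through the end of pregnancy".
- **Comparator (9.2.4.1, repeated in 9.3.1).** "Documentation of no exposure to any CGRP mAb from 5 half-lives prior to LMP or at any point during the patient's pregnancy".
- **Exposed cohort (9.2.4.1).** "Documentation of exposure to erenumab-aooe from 3 months prior to LMP or at any point during the patient's pregnancy". Section 9.3.1 has the same open end, with a 16-week start. The differing start is a separate matter.
- **Use of these definitions (9.3.1).** "The following criteria will be used to assign women to 1 of 2 cohorts, as determined by exposure to erenumab-aooe".
- **Timing of entry.** Women enroll while pregnant with the outcome unknown (9.2.4.1). Section 9.2.1 says "women should be enrolled in the study as soon" as the pregnancy is known.
- **Timing of the check.** Appendix E schedules the inclusion and exclusion criteria at enrollment only. Erenumab start and stop dates are then updated at about 14, 21 and 34 weeks (9.2.8).
- **Analysis set (Table 5).** The Full Analysis Set keeps every enrolled woman with any data.
- **Spontaneous abortion (9.7.2.4).** The prevalence comes from "dividing the number of fetal losses occurring before 20 weeks gestation by the total number of pregnancies". Section 9.7.2.5.1 compares cohorts by risk ratio. Section 9.7.2.1 runs analyses overall, on ever-exposed status, and by earliest trimester of exposure.
- **Malformations.** The analysis rests on first-trimester exposure, from LMP to 14 weeks (9.7.1.2, 9.7.2.6).

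**The concern.** Neither the comparator definition nor the exclusion can be settled on the day a woman enrolls, because both depend on what she takes afterwards. Read literally:

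- A comparator woman who starts erenumab at 25 weeks stops meeting the comparator definition and meets the exposed one.
- A woman with first-trimester erenumab who is given another CGRP antibody at 30 weeks meets the exclusion, although her first-trimester exposure is what the primary analysis needs.

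A woman must still be pregnant to start a drug late. One first dosed after 20 weeks has passed the window in which a loss counts as a spontaneous abortion. Placing her in the exposed denominator, and out of the comparator's, gives the exposed cohort event-free time that it did not earn under exposure. In a safety registry, a ratio biased toward protection is false reassurance.

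For malformations, the late starter is validly unexposed in the first trimester. She nevertheless fails the comparator definition and has no first-trimester exposure, so she falls out of the primary contrast. The later switcher is lost through the exclusion.

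**Working it through.** **1. The plan's own size.** Inputs from 9.5: 3% versus 6%, 80% power, α = 0.05 (taken as two-sided), 1:1 allocation. With the pooled-variance formula for two proportions and mean proportion 0.045:

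n = [1.960·√(2·0.045·0.955) + 0.842·√(0.03·0.97 + 0.06·0.94)]² / 0.03² ≈ 749 live births per group.

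Enrollment = 749/(0.85·0.62) = 1421. Both match Table 4, so the sample size calculation is not at fault.

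**2. Early loss with late starters moved to the exposed cohort.** Take N = 1421 per cohort, the same true loss risk p in both, and a share s of continuing comparator pregnancies that start erenumab after 20 weeks. Neither p nor s is in the protocol.

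- Exposed risk = p / [1 + (1−p)s]
- Comparator risk = p / [1 − (1−p)s]
- Ratio under no effect = [1 − (1−p)s] / [1 + (1−p)s]

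N cancels. With p = 15%:

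| s | Exposed | Comparator | Null RR |
|---|---|---|---|
| 2% | 14.7% | 15.3% | 0.97 |
| 5% | 14.4% | 15.7% | 0.92 |
| 10% | 13.8% | 16.4% | 0.84 |

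The result depends little on p. At s = 5% the null RR is 0.909, 0.914 and 0.918 for p = 5%, 10% and 15%.

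**3. The earliest-trimester results.** These take late starters out of the first-trimester exposed group. If the comparator definition is applied literally, however, those women are still missing from the comparator. The null RR is then 1 − (1−p)s, which at p = 15% is 0.983, 0.958 and 0.915 for s = 2%, 5% and 10%. About half of the distortion remains.

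**4. Exclusion for another CGRP antibody.** Let eE and eC be the shares of continuing pregnancies excluded from the exposed and comparator cohorts. The null RR is [1 − (1−p)eC] / [1 − (1−p)eE]. With p = 10%:

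- comparator only, 3%: 0.97
- both cohorts, 3%: 1.00
- exposed only, 3%: 1.03

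A mixed case, with 2% moved, 10% of exposed excluded and 2% of comparators excluded, gives (1 − 0.9·0.04)/(1 − 0.9·0.08) = 1.04. Exclusion therefore has no fixed direction.

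**5. Malformations.** Losing 5% of live births in both groups leaves about 712 per group and 78.0% power; restoring 749 would need 749/(0.85·0.62·0.95), or 1497 enrolled per group. Losing 10% leaves about 674 and 75.8% power, with 1580 needed.

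**The case against.** Several points on the other side stand.

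- **Removal is not described as a procedure.** A reader might infer that the protocol orders enrolled women to be dropped or moved. It does not. Appendix E puts the check at enrollment, Appendix F lists eligibility as baseline items in the past tense, the reasons for ending follow-up (9.1) do not include starting a CGRP antibody, and Table 5 keeps enrolled women with data. What stands is a conflict between these passages and open-ended definitions that 9.3.1 uses to assign cohort.
- **No net direction for exclusions.** A reader might infer that every late exclusion favors erenumab. Step 4 shows otherwise: excluding exposed women who switch pushes the ratio above 1.
- **No evidence that removal depends on the outcome.** Section 9.9.1.2 says women "may also have changed their exposures after learning of the outcome", which might be read as support. That sentence concerns women informed before enrollment, as a source of recall bias. It does not say that enrolled women start a CGRP antibody after a fetal finding.
- **The share may be small.** Section 7.1 reports improvement or remission in 83% of women with migraine without aura in the second trimester and 87% in the third, so late starts may be uncommon. Migraine with aura improves less.
- **The primary endpoint is largely protected,** because malformations are analyzed on first-trimester exposure.
- **Mitigations are planned.** There are results by earliest trimester, and 9.7.2.6 adds analyses of exposure timing, a time-varying Cox model, and spontaneous abortion by gestational age at enrollment. Those in 9.7.2.6 are sensitivity analyses that depend on sufficient numbers, and none changes the main ever-exposed ratio.

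Details of time-varying modeling can be left to the SAP. Eligibility, cohort assignment and the main contrast are fixed in the protocol and, followed as written, bias the ever-exposed ratio.

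**Conclusion.** The point holds, mainly for a secondary outcome. The overall ever-exposed risk ratio for spontaneous abortion treats women first dosed after the loss window as exposed. That is immortal time, and it biases the ratio toward protection: about 0.97, 0.92 or 0.84 under no effect if 2%, 5% or 10% of continuing comparator pregnancies start erenumab after 20 weeks and are counted as exposed. These shares and the 15% loss risk are assumptions. If few women start late, the bias is small.

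Exclusion for another CGRP antibody can bias either way, depending on which cohort loses more women. For malformations the cost is mainly the loss of women with valid first-trimester status: power of about 78% rather than 80% if 5% of live births are lost in both groups. The documents do not establish that enrolled women will actually be removed, only that the definitions imply it while other passages keep them. The passages must be reconciled.

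**What to change.** 1. In 9.2.4.1, 9.2.4.2 and 9.3.1, state that the CGRP eligibility criteria are assessed up to enrollment and that enrolled women are not removed for later use. Align Table 5 and Appendix F. The exposed-cohort item in Appendix F also admits any other CGRP antibody, which contradicts 9.2.4.2.
2. For malformations, classify women by exposure through the end of the first trimester and keep later starters and switchers in that class.
3. For spontaneous abortion, make the main comparison one in which only erenumab exposure before the event counts, either time-updated or up to the end of the loss window. Time-updating is cleaner, because a fixed cutoff still credits a woman who starts within the window with her earlier event-free weeks. Do not leave this to a sensitivity analysis that depends on numbers.
4. Record later use of another CGRP antibody as a co-exposure, with a sensitivity analysis.

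The cost is protocol wording and some programming. Erenumab and other medication dates are already collected at each pregnancy contact, and the 749 live births and 1421 enrolled per group do not change. The downside is that a few women with mixed late-pregnancy exposure remain in each cohort.

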#### 9.2.5 Matching

Matching is currently not planned, but if sufficient sample size allows, propensity score matching may be explored ([Section 9.7.2.5.1](#)).

#### 9.2.6 Data Collection

The reporter of information can be the patient, patient's HCP, or infant's HCP where applicable (see [Study Design Schema](#)). "Information" includes all variables described in [Section 9.3](#). Where the HCP is unavailable, the patient can report the necessary information to the study CC staff for entry into the eCRF. Where information is reported in duplicate and there is a discrepancy, the HCP reported information will take precedent. Migraine diagnostic and treatment information should be collected and/or confirmed by the treating migraine specialist (neurologist) or PCP (ie, preferably not the OB, nurse midwife, or patient). However, the patient is considered a suitable source for reporting some migraine history characteristics, including their average monthly migraine days and age at migraine onset. Any reported outcome of a major or minor congenital malformation will be adjudicated.

#### 9.2.7 Baseline Period

The baseline period is defined as the first date of data collection after patient informed consent has been signed. Data collected for baseline assessments will be a specific time point consistently for all enrolled patients (eg, the baseline data collection period for current pregnancy information will be defined as at the time since LMP, while co-medication use will examine all available medications classified as current or prior use starting from 3 months prior to LMP). Baseline information will be collected to confirm patient eligibility, collect relevant medical history, and characterize the current pregnancy status of the patient. The following covariates will be collected:

- Documentation of informed consent
- Reporter of information (eg, patient, PCP, OB, neurologist [indication specialist], nurse midwife, other)

- Inclusion/exclusion criteria
- Patient demographics and characteristics (eg, age of mother, education level, race/ethnicity, height, pre-pregnancy and current pregnancy weight)
- Lifestyle risk factors (eg, smoking, caffeine consumption, alcohol use, illicit drug use)
- Current pregnancy information (eg, LMP, gestational age at enrollment, estimated date of delivery [EDD], date and results of any prenatal tests, date and results of any pregnancy complications)
- Medical history:
  - Pregnancy history (eg, parity, gravidity, previous preterm births, previous spontaneous abortions or elective or therapeutic terminations, reason for any elective or therapeutic termination, history of congenital malformations)
  - Medical history and comorbid conditions: surgical and medical history/significant maternal medical conditions other than migraine (eg, diabetes, high blood pressure)
  - Migraine history including: average monthly migraine days before pregnancy, number and duration of migraines and migraine days in the past month (patient-reported), age at migraine onset, type(s) of migraine (chronic, episodic), presence of aura, age at migraine onset, number of prior preventive migraine treatment failures (pre-pregnancy), days of acute migraine treatments each month (pre-pregnancy and by trimester), impact of pregnancy on the intensity of headache
    - If diagnosed with chronic migraine, age at chronic migraine onset
  - Family reproductive history (eg, multiple births, pregnancy complications [ie, preeclampsia, pregnancy-induced hypertension, preterm labor, gestational diabetes, placenta previa], congenital malformations, spontaneous abortions, premature births, chromosomal anomalies, evidence of developmental delays)
- Erenumab-aooe treatment (including start and stop dates, dose, dosing frequency, reason for discontinuation [if applicable])
- Current and prior medication use starting from 3 months prior to LMP through pregnancy including presence of any other prescription migraine treatments, other over the counter (OTC) migraine treatment(s), folic acid and other vitamins, herbal remedies or supplements, vaccinations, or other medications used to treat chronic conditions or comorbidities; including start and stop dates (if applicable)
- Patient adverse events (AEs) and serious adverse events (SAEs) (including event, start date, ongoing or end date, seriousness, severity, relationship to erenumab-aooe, outcome, action taken)

